### **Participant recruitment for Aim 3 (UH3 Phase, 2019-2021).**

Based on preliminary data, burden of opioid-related illness, and familiarity with supportive local stakeholders, we selected La Crosse County, Marathon County, and Brown County as the implementation sites for this study. Eau Claire, Douglas, and Outagamie Counties will serve as the

nonintervention sites, where participants will receive services as usual. In the fall of 2019, 3 full-time Prevention Navigators were hired and trained to conduct the intervention. Participants in this phase of the study will be recruited into one of two groups, Prevention Navigation, or usual services. Beginning in year 3, SSP clients at the 6 selected Vivent Health sites will be notified about the study by prevention specialists or SSP staff if the client 1) tests for HCV or HIV at the SSP, 2) inquires about services that may be in the prevention home through casual conversation, 3) the client engages in naloxone training, 4) through posted materials of the availability of new resources for improving prevention services and linkages to treatment in the SSP and community offices, 5) recruit through flyers and posted materials in the SSP and local community resource offices, and public areas, 6) through Vivent Health Facebook advertisements, 7) through our study website listed on our flyers, and/or 8) through respondent-driven sampling (RDS). Upon the completion of the first two attended Prevention Navigation sessions,

participants will be given a referral coupon and asked to refer one eligible peers per coupon to participate in the study. Vivent Health will dispense coupons that have been prepared by UW research staff. SSP clients at the nonintervention sites will be recruited at the time the Vivent Health staff member assists them with regular exchange services. Nonintervention sites will aim to enroll about one participant every-other week.

[figure not shown]
[figure not shown]

Figure 5. Parallel crossover (wait-list control) and cross-site study design

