**Survey and needs assessment.** The primary source of data collection in all three groups of the study will be from the ACASI questionnaire, administered at 0 months (baseline), 3 months, and 6 months from enrollment. All surveys will be administered on a tablet using the ACHESS application, by the participant accessing the survey in ACHESS on their smartphone or web browser on their own time, or over the phone. The data will be securely stored at UW-Madison and erased from the tablet if

applicable. The survey will consist of multiple choice questions designed to efficiently assess drug use history, access and utilization of prevention services, readiness for intervention, and injection related risk behaviors. The final survey a participant takes will include exit questions to help us evaluate and improve the program. Participants enrolled in the intervention between February 1, 2023 and March 31, 2023 will complete the baseline and 3 months ACASI questionnaire only.

**ACHESS.** All participants will complete study assessments using the ACHESS application. ACHESS can be accessed by downloading the application to a smartphone or via a web browser. Participants may also take part in optional non-research activities within the ACHESS app. These activities include: 1) posting on discussion boards, 2) utilizing the private message function to communicate with study staff or other participants, 3) viewing local community resources and their contact information, 4) viewing and saving motivational quotes of the day and logging thoughts of gratitude, and 5) accessing study staff contact information.

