## **7.0 STATISTICAL CONSIDERATIONS**

**Sample size and power considerations for Aim 1.** Power to detect a significant impact of the client-centered prevention home model is based on the change in proportion of clients in the 3 target counties who receive the 9 essential services (see Table 1, pg. 2) compared to clients in the 3 non-targeted counties. The design effect for respondent-driven sampling is a complex function of the network structure in the population, and thus, it is difficult to precisely estimate the sample size requirements. Nevertheless, simulation research indicates that the design effect for respondent-driven sampling is likely to be 2 or less, which suggests that a sample twice that of simple random sampling should provide adequate power. We estimate that approximately 10% of all clients will have access to all 9 essential services prior to the study. Applying a design effect of 2, and given a sample size of 800-1200 clients, the study will be powered to detect an increase in service provision of 8-10% (424 subjects per group is sufficient to detect a 10% difference in essential service provision rates; 582 subjects per group is sufficient to detect an 8% difference), assuming 80% power and 5% type I error.

**Sample size and power considerations for Aim 3.** The complexity of our study design requires multiple longitudinal approaches to account for independent and dependent samples. Based on our formative work, an average of 2 clients enrolled per week into the study is feasible for the SSP staff.

With a sample size of 405 (270 intervention and 135 controls), we would have 80% power to detect a difference between 28% and 42% in the same outcome, an effect size that we believe is meaningful and realistic to achieve. In other words, the sample size was chosen to ensure that the Primary Aim 1 comparisons of “Strongly Agree” vs all others of a factor would have sufficient power to detect clinically meaningful increases in accessibility. To address Primary Aim 1, we used preliminary data from the first phase of the study to assume that the base rate of a participant who will strongly agree that it is easy for them to access addiction treatment services is 26%.

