## **D. Protection of Incarcerated Individuals**

For Aim 3, our program is a 12-week intensive case-management program. Therefore we want to ensure that participants who become incarcerated have a way to re-engage with the study and intervention once they are released from jail or prison. If it is learned that a research participant is incarcerated at any time in the study, they will be immediately un-enrolled and research activities will be suspended. Participants in the intervention arm may receive contact from the prevention navigator to notify them of this and explain the process. No data will be collected from the participant during this time. Upon release, participants may contact Vivent Health staff to re-enroll in the study. The consent document will be reviewed with the participant at this time to re-assess willingness to participate. Participants can take their assessment after 2.5-5.5 months from baseline or follow up assessment. If the opportunity to take the assessment is no longer available, then we treat it as missing.

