## **L. Incentives**

**Aim 1 and 2.** Participants will receive \$20 remuneration for survey participation on the day of enrollment, and will receive a smaller incentive of \$10 for each eligible peer recruit who enrolls in the study. For participants who have a reactive HCV rapid test and are unable to provide a blood sample for HCV confirmatory testing due to phlebotomy difficulties, a one-time incentive of \$10 will be provided if they return at a later date and attempt a second blood draw. Syringe program clients and local service providers who agree to participate in qualitative interviews will be paid an incentive of

\$30 each for one hour-long interview. All primary care providers who are selected to participate in the quantitative mail-based survey will receive an incentive of \$5 at the time the survey is mailed to them.

**Aim 3.** Participants will receive \$20 remuneration for survey participation and rapid testing on the day of enrollment, and will receive an additional incentive of \$20 for 3-month, and 6-month assessments. Participants may also receive a monthly incentive of \$5 to update their contact information so we have the most up to date information to decrease the risk of loss to follow up if it is deemed necessary to do so. For participants who have a reactive HCV rapid test and are unable to provide a blood sample for HCV confirmatory testing due to phlebotomy difficulties, a one-time incentive of \$10 will be provided if they return at a later date and attempt a second blood draw. Additionally, participants will receive \$10 for each eligible peer recruit who enrolls in the study.

**COVID-19 Pilot.** Participants will receive \$10 for each research assessment (baseline, 4 weeks, and 30-days post service resumption). There will be no incentives for testing during this sub-phase of the study.

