The goal of the Client-Centered Prevention Home program is to increase the knowledge of people who inject drugs on navigating prevention and treatment services for HIV, HCV, and drug overdose. We describe measures for our study population in the Appendix. Key sources for measurement will come from the ACASI survey that will be adapted from the ROI Harmonized UG3 survey, surveillance data gathered from the state of Wisconsin, and Medicaid health utilization data.

**1.4. Study data collection sites.** The main community partner, Vivent Health, will serve as the data collection and study site. Vivent Health is a statewide organization that provides harm reduction services, including syringe services and confidential HIV and HCV testing. As shown in Figure 1, three sites will be used for the intervention of the study: Brown County (Green Bay), Marathon County (Wausau), and La Crosse County (City of La Crosse). The 3 other Vivent Health offices that participated in the UG3 study phase, including Outagamie County (Appleton), Eau Claire County (City of Eau Claire), and Douglas County (Superior), will serve as recruitment sites for control group participants during the UH3 phase, but will not provide the prevention navigation intervention.

**1.5. Study sample description and inclusion and exclusion criteria.** Leveraging relationships developed among Vivent Health clients and community partners during the UG3 phase, we will recruit participants using Vivent Health staff at all six counties. In order to be part of the study, participants must meet the following eligibility criteria: 1) clients must be at least 18 years old, 2) have injected drugs to get high in the past 30 days, and 3) reside in one of the participating communities in or around one of the six participating counties.

Exclusion criteria are: (1) not speaking English fluently, (2) residing outside or being unwilling or unable to travel for study visits at one of the participating communities.

**1.6. Sample size.** A total of 405 participants will be enrolled to evaluate the intervention (Figure 1). Study procedures will vary for participants based on enrollment into 2 study groups, as follows:

- (a) 270 participants enrolled at intervention sites, who will receive prevention navigation.
- (b) 135 participants enrolled across the 3 non-intervention sites, who will serve as a contemporaneous control group.

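### Aim 3's 80% power holds, with no margin, only for an unadjusted test of 405 independent, fully observed people; the plan states no allowance for loss, site or peer referral, and leaves 28% unreconciled with its 26% base rate

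*Combined protocol and SAP*

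**What the plan says.** The Aim 3 paragraph of Section 7.0 opens by saying that the design needs several longitudinal approaches, for independent and for dependent samples. It then states: "With a sample size of 405 (270 intervention and 135 controls), we would have 80% power to detect a difference between 28% and 42" percent. A few lines later it reports, from first-phase data, that the assumed base rate of participants who "strongly agree that it is easy for them to access addiction treatment services is 26" percent. It does not say where 28% comes from. It names no alpha, sidedness, test, time point, retention, ICC or design effect.

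Other parts of the plan bear on that figure:

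- **405 is the number enrolled.** Appendix 1, section 1.6: "A total of 405 participants will be enrolled to evaluate the intervention", split into 270 at intervention sites and 135 at non-intervention sites.
- **Arm is set by site.** Section 4.0 (recruitment for Aim 3) and Appendix 1, section 1.4, name three intervention counties and three comparison counties.
- **Peer referral is one of eight recruitment routes** (Section 4.0), paid per enrolled recruit in Aim 3 (Section 9.0, Incentives).
- **Missing assessments are expected.** Section 5.4: "Participants enrolled in the intervention between February 1, 2023 and March 31, 2023 will complete the baseline and 3 months ACASI questionnaire only". Section 9.0 D, on incarceration: "If the opportunity to take the assessment is no longer available, then we treat it as missing". Section 9.0, Incentives, allows a monthly contact payment "so we have the most up to date information to decrease the risk of loss to follow up".
- **Aim 1 is treated differently.** The paragraph just above does make an allowance: "Applying a design effect of 2, and given a sample size of 800-1200 clients". It also states a 5% type I error.
- **Analysis.** Section 6.0 plans generalized linear mixed models for Aim 3 and names no site term.

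**The concern.** The 270 versus 135 figure is the only power statement for the between-site comparison, labelled (B) in Appendix 1, section 1.7. If it assumes complete and independent data, it describes a study with less missing data and less clustering than the one the protocol sets out.

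Two things are then unclear to a reader: whether 405 enrolled people leave room for any loss, and what difference a comparison of three sites with three can be expected to detect. The unexplained pair of rates adds to this, because the answer depends on which rate and which target are meant.

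**Working it through.** **Inputs.** Control n0 = 135, intervention n1 = 270, p0 = 0.28, p1 = 0.42 (Section 7.0, Aim 3). Alpha of 5% is borrowed from the Aim 1 paragraph and two-sidedness from the COVID-19 pilot paragraph, because Aim 3 states neither. Loss rates, ICCs, an Aim 3 design effect and a baseline correlation are not in the documents; those below are assumptions shown over a range.

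**Formula (pooled).** Power = Φ{[(p1 − p0) − 1.96·SE0] / SE1}, where SE0 = √[p̄(1 − p̄)(1/n0 + 1/n1)] and SE1 = √[p0(1 − p0)/n0 + p1(1 − p1)/n1].

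**Step 1: the plan's own figure.**
- p̄ = (135 × 0.28 + 270 × 0.42)/405 = 0.3733; SE0 = 0.0510; SE1 = 0.0489.
- Pooled: (0.14 − 1.96 × 0.0510)/0.0489 = 0.819, so power = 0.794.
- Unpooled: 0.14/0.0489 − 1.96 = 0.900, so power = 0.816.

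The stated 80% reproduces. Solving the pooled formula for 80% at 1:2 gives about 412 complete people, against 405 enrolled. The unpooled version leaves room for about 4% loss. Either way there is essentially no margin.

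**Step 2: loss to follow-up**, equal in both arms, n0 = 135(1 − d) and n1 = 270(1 − d), 28% versus 42%:

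| Assumed loss d | n0 / n1 | Power |
|---|---|---|
| 5% | 128.25 / 256.5 | 0.77 |
| 10% | 121.5 / 243 | 0.75 |
| 20% | 108 / 216 | 0.70 |
| 30% | 94.5 / 189 | 0.64 |

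**Step 3: site clustering, no loss.** Design effect = 1 + (m − 1)·ICC, with m = 135/3 = 45 control and 270/3 = 90 intervention participants per site:

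| Assumed ICC | Design effect, control / intervention | Effective n0 / n1 | Power |
|---|---|---|---|
| 0.005 | 1.22 / 1.45 | 110.7 / 186.9 | 0.68 |
| 0.01 | 1.44 / 1.89 | 93.8 / 142.9 | 0.59 |
| 0.02 | 1.88 / 2.78 | 71.8 / 97.1 | 0.46 |

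**Step 4: peer referral.** Section 4.0 hands out coupons after the first two navigation sessions, which control participants do not have. A design effect of 2 in the intervention arm only gives an effective 135 versus 270/2 = 135, and power 0.68. This is an upper case: Section 7.0 puts the value for respondent-driven sampling at 2 or less, and referral is one route of eight.

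**Step 5: detectable difference** at 80% power from a 28% base: 14.1 points as stated, 15.9 with 20% loss, 17.9 at ICC 0.01.

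**Step 6: credit for baseline adjustment.** At an assumed baseline correlation of 0.5, the variance is multiplied by 1 − 0.5² = 0.75. With 20% loss, power for 28% versus 42% returns to 0.82.

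**Step 7: the two base rates**, all 405 analysed: 26% versus 40% (the same 14 points) gives 0.804; 26% versus 42% (16 points) gives 0.895.

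**The case against.** The strongest reply is that the arithmetic is right and that a longitudinal analysis is planned. The paragraph opens with dependent samples, Section 6.0 specifies mixed models, and adjustment for baseline can offset moderate dropout, as Step 6 shows. This stands as far as it goes, so it would be wrong to say that 405 cannot tolerate loss under any analysis. But the figure given is that of a plain two-sample test. The paragraph claims no gain from repeated measures and gives no within-person correlation, and neither section mentions a site effect.

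The missing-data evidence is also limited. The planned gap at month 6 affects only intervention enrollees from a two-month window. It costs nothing if the target is month 3, and the paragraph names no time point. Participants released from incarceration may re-enrol and have an assessment window. These provisions show that loss is expected but not how much, which is why a range is shown.

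Three stronger readings are tempting, and the documents do not support them:

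- *28% is an error for 26%.* The text never calls 28% the base rate. It may be an expected control rate at follow-up. At the same 14 points the mismatch hardly matters, and the pairing of 26% with 42% does not appear in the plan.
- *A design effect of 2 applies to both arms*, which would take power to 0.49. The Incentives section words the payment generally, but coupons follow navigation sessions that only the intervention arm receives.
- *405 is too small.* With no stated loss rate, ICC or correlation, the documents cannot show that.

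**Conclusion.** The point holds as a gap in the stated assumptions and an unreconciled input; it is not an arithmetic error. The 80% for 28% versus 42% is correct for an unadjusted test of 405 independent, complete observations and has essentially no margin. The plan's own between-site design departs from each of those conditions, and Section 7.0 makes no allowance for any of them.

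The size depends on assumed values. Each source taken alone, without adjustment, moderate loss takes power into the 0.6s or 0.7s, and even a small site ICC takes it below 0.7. Baseline adjustment could restore about 0.8 at 20% loss if the correlation is 0.5. The choice of base rate matters only through the target: negligible at 14 points, about 10 percentage points of power if 42% is kept with 26%.

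The within-person comparison, (A) in Appendix 1, section 1.7, is not affected by site assignment, and the 270 versus 135 figure does not describe it. The point should be fixed, and the sample size need not change.

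**What to change.** Keep 405. In the Aim 3 paragraph of Section 7.0:

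1. Say what 28% is and reconcile it with 26%. Name one target difference, one time point, alpha and sidedness.
2. Restate the power, or the detectable difference, for the between-site comparison under a stated retention and a stated allowance for site and for peer referral. Where a value is unknown, show a short range.
3. Credit baseline or repeated-measures adjustment only if the Aim 3 model uses it, and state the correlation assumed.

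In the Aim 3 analysis text of Section 6.0, add one sentence saying whether the between-site result accounts for the six sites in its standard errors or is conditional on these six sites.

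The cost is one rewritten paragraph and one sentence, with no extra participants. The drawback is that the stated power will probably look less favourable. Accounting for the sites would also widen the between-site intervals; the conditional alternative makes a narrower claim.

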Clients at the nonintervention sites who are determined to be eligible after SSP staff administer the screening questionnaire will have their name and date of birth collected and assigned a study ID number. The SSP or UW staff member will go through the study procedures and read a verbal consent script over the phone, by video conference, or in-person. They will be required to answer T/F questions regarding the consent before giving verbal consent. A locator form will be filled out at this time. Rapid testing for HIV and hepatitis C will be conducted by the SSP staff member using the same standard procedures as above. The data collection forms will again be shared with the research team securely after each research assessment.

All clients who are determined to be eligible will have a SSP or UW staff member go through the ACHESS specific activities (surveys and option activities) and read a verbal consent script over the phone, by video conference, or in-person. The participant will be required to provide verbal consent.

**COVID-19 Pilot Intervention.** Participants will be recruited to the virtual prevention navigation implementation pilot program through three avenues.

- 1) Participants who participated in phase 1 and consented to future contact will be recruited for the study
- 2) Clients who access current SSP services will receive a flyer in their safe injection supply bags with contact information to call if interested in the study
- 3) SSP staff may engage clients about the study if a client calls into the SSP asking for services

Participants will be eligible for enrollment if they are 18 years of age or older, have injected drugs in the past month, reside in a rural WI community, and can speak and understand the English language. Clients will speak with the Prevention Navigator to determine eligibility, consent to the study, and schedule their first navigation session. If the client agrees to participate, their name, DOB, county and zip code of residence, and phone number will be collected. Navigators will have a case load of no more than 15 participants at one time to ensure workload is manageable, with a final recruitment

number of n=108 intervention participants and n=108 control participants. Navigators may take down a client's phone number, per Vivent Health policy, in order to contact the individual when spots open.

We will pause recruitment for our originally proposed UH3 protocol until at least Sep 2020 when the pilot has ended.

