### **Data Analysis for COVID-19 Pilot Cohort.**

The objectives of the analysis are consistent with the UH3 study design to evaluate the influence of virtual prevention navigation on progress toward a number of health goals. However, given the restricted timeline for prevention navigation with two assessments one month apart, we will assess pre-and post-changes in factors associated with the risk of HCV, HIV, and overdose death among PWID.

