**COVID-19 Pilot.** Given the uncertainty of the timeline for prevention navigation, it is unclear how large our sample size will be. Understanding that there will be two assessments one month apart, we will use matched pair t-test to assess differences between the first and second assessments. Using the same process as above, comparisons of “Strongly Agree” vs all others of a factor would have sufficient power to detect meaningful increases in accessibility. We expect a total sample size of 216 PWID, which provides adequate statistical power (0.83) to detect a 20% difference between three time points of interest (two-sided alpha=0.05).

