**1.7. Study design.** In order to measure the impact of the Client-Centered Prevention Home we will prospectively assess the 12-week intervention by measuring outcomes at baseline, 3-months, and 6-months. We will target participants who engage in syringe services at Vivent Health and may be interested in additional services that may be offered in our multilevel harm reduction intervention. At intervention sites, the Prevention Navigator will engage prospective clients by screening them for the study, having the participant sign the consent form and performing baseline assessments along with rapid testing for HIV, HCV, and syphilis. Using the same infrastructure used in the UG3 phase, a second group of controls will be enrolled at the three non-intervention sites. Syringe service program staff at the non-intervention sites will recruit participants for baseline, 3-month, and 6-month assessments during the two year study period.

The health-related goals for PWID in the context of this study are multi-faceted, reflecting the heterogeneous needs of this vulnerable population. Accordingly, there is not a single, primary outcome which can be measured to evaluate the impact or effectiveness of the intervention. We therefore have proposed a study design that allows us to evaluate the influence of prevention navigation on progress toward a number of health goals. Because no single study design can account for all of the biases inherent in a non-randomized, multi-county intervention trial, we have proposed 2 different types of comparisons in our evaluation strategy:

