**(B) A comparison of participants enrolled at sites with and without prevention navigation**

In separate analyses, we will compare the self-reported outcomes of individuals enrolled at Vivent Health offices offering only standard prevention services without prevention navigation. This is advantageous for detecting changes over 6 months of follow-up.

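### The COVID-19 pilot plans 108 controls but states no comparison with them; its only named test is within-person, and the 0.83 power figure does not match that test

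*Combined protocol and SAP*

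**What the plan says.** Section 4.0 (COVID-19 Pilot Intervention) sets a final recruitment "number of n=108 intervention participants and n=108 control participants". Section 6.0 (Data Analysis for COVID-19 Pilot Cohort) describes the objectives as in line with the UH3 design, namely to "evaluate the influence of virtual prevention navigation on progress toward a number of health goals". It then says that, because the timeline is short and there are two assessments a month apart, "we will assess pre-and post-changes in factors associated with the risk of HCV, HIV, and overdose death among PWID".

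Section 7.0 (COVID-19 Pilot) names one test: "we will use matched pair t-test to assess differences between the first and second assessments". It continues with "Using the same process as above", dichotomises the item as strongly agree against all other answers, and expects a "total sample size of 216 PWID, which provides adequate statistical power (0.83) to detect a 20% difference between three time points" at two-sided alpha 0.05.

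For the main Aim 3 study, Appendix 1 section 1.7 gives a reason for using more than one comparison: "Because no single study design can account for all of the biases inherent in a non-randomized, multi-county intervention trial". Its comparison (B) then says "we will compare the self-reported outcomes of individuals enrolled at Vivent Health offices offering only standard prevention services without prevention navigation". The pilot sections contain no equivalent sentence.

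**The concern.** The objective is evaluative and a concurrent control group of equal size is planned, yet the named test uses each person only as their own control. A paired test measures the whole change between the first and second assessments. It cannot separate navigation from anything else that altered access in that month. Section 1.6 describes services and access as disrupted at the time, so stable access cannot be taken for granted. Improving access would be read as a benefit of navigation, and worsening access would offset a real benefit.

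The controls are counted in the 216 behind the power statement, since 108 + 108 = 216. They therefore have a role in the sample size but no stated role in the analysis. The power sentence also refers to three time points, while the test beside it uses two assessments.

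**Working it through.** **Inputs.** From Section 7.0: two-sided alpha 0.05, total 216, stated power 0.83, a 20% difference, and the strongly-agree dichotomy. Also from Section 7.0, under Aim 3: a base rate of 26%, and 28% as the lower proportion in the Aim 3 power calculation. From Section 4.0: 108 per arm. Assumed here, because the documents give no value: within-person correlation r of 0 to 0.5, the size of any drift, and 20% dropout (0.8 × 108 ≈ 86 per arm).

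**1. Reproducing 0.83.** Two readings reach it.
- Paired t-test at 0.20 SD on all 216 people: noncentrality 0.20 × √216 = 2.94, power 0.833. On the 108 navigated people alone, 0.20 × √108 = 2.08, power 0.54.
- 108 vs 108 comparison of proportions with continuity correction: power = Φ[(0.20 − 1/108 − 1.96·SE₀)/SE₁]. For 26% vs 46%, SE₀ = 0.0653 and SE₁ = 0.0639, giving Φ(0.98) = 0.837. For 28% vs 48% it is 0.828. Without the correction the values are 0.870 and 0.862.

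The text does not say which calculation was used.

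**2. The named test at 20 percentage points.** Variance of the within-person change: V = p₁(1−p₁) + p₂(1−p₂) − 2r√[p₁(1−p₁)p₂(1−p₂)]. Noncentrality is (p₂−p₁)√n/√V.
- 26% to 46%, r = 0: V = 0.1924 + 0.2484 = 0.4408, noncentrality 3.13 on 108 pairs, power 0.873.
- Same change, r = 0.5: V = 0.2222, noncentrality 4.41, power 0.992.
- 28% to 48%, r = 0: power 0.866.

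The range is therefore 0.87-0.99 on 108 pairs, and at least 0.99 on 216. Neither gives 0.83.

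**3. What drift does to the paired test.** Same formula, 108 people, no navigation effect:

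| Drift | Base rate | r = 0 | r = 0.3 | r = 0.5 |
|---|---|---|---|---|
| 5 points | 26% | 0.127 | 0.162 | 0.208 |
| 5 points | 28% | 0.124 | 0.157 | 0.201 |
| 10 points | 26% | 0.354 | 0.473 | 0.609 |
| 10 points | 28% | 0.344 | 0.460 | 0.595 |

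A valid test would reject 5% of the time in every cell.

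**4. Between-arm alternatives, 20-point effect, controls flat.**
- Difference in change: SE = √[(V_navigated + V_control)/n]. At base 26%, r = 0, n = 108: V_control = 2 × 0.26 × 0.74 = 0.3848, SE = √(0.8256/108) = 0.0874, and Φ(0.20/0.0874 − 1.96) = 0.63. At r = 0.5, SE = √(0.4146/108) = 0.0620, giving 0.90. Over both base rates, power is about 0.61-0.90 at 108 per arm and 0.51-0.82 at 86 per arm.
- Second assessment adjusted for the baseline outcome (linear model, 20,000 simulations per cell, equal baselines): 0.86-0.95 at 108 per arm and 0.78-0.89 at 86.

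**5. Error rates of the alternatives with no navigation effect.** With equal baselines and equal drift of 0, 5 or 10 points, the adjusted contrast rejects 4.5-5.4% of the time. With an assumed stable baseline gap of 26% vs 36%, no drift and 108 per arm, it rejects about 35%, 21% and 15% at r = 0, 0.3 and 0.5. Difference in change stays near 5% in those same cases.

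**The case against.** The best defence is that a control comparison is implied. Section 6.0 ties the pilot's objectives to the UH3 design, which includes one. The reason it gives for departing, two assessments a month apart, explains dropping growth models on quarterly data but not dropping the controls, since pre/post changes can themselves be compared between arms. The words "Using the same process as above" follow the Aim 3 calculation for 270 intervention and 135 control participants, and 0.83 can be reproduced as 108 vs 108. This stands to the extent that a reader who infers that the pilot deliberately abandoned the control comparison goes beyond the text, which is ambiguous. It still leaves no stated between-arm test or model.

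A reader might also infer that pilot controls would not be assessed at all, because Section 5.4 sets assessments at the first and last navigation session. Section 9.0 L (Incentives) gives baseline and 4 weeks for pilot participants, which controls could follow. The need is to confirm it.

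A third inference would be that adjusting for baseline restores a 5% error rate whenever drift is equal. No passage describes random allocation, and step 5 shows that the claim fails if the arms start from different rates that the covariates do not explain.

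Finally, this is a short pilot, Section 7.0 admits uncertainty about its size, and the drift figures are hypothetical. Those points limit the weight of the numbers, not the gap in the plan.

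**Conclusion.** The concern holds as a gap in the analysis plan. The pilot intends to evaluate navigation and plans 108 controls, but specifies only within-person change. Followed as written, it would attribute to navigation any other change in access over the month. The 12-21% and 34-61% rejection rates are conditional illustrations. They rest on assumed drifts of 5 and 10 points, a 26-28% base rate taken from Aim 3, correlation 0-0.5 and no dropout. The documents do not show that drift of this size occurred.

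The power sentence is internally inconsistent: three time points against a two-assessment test, and 0.83 against 0.87 or more for that test at 20 percentage points. It would be tempting to call 0.83 an arithmetic error. The documents do not support that, because two other readings reproduce it. This should be fixed before the pilot is used to support any statement about a navigation effect.

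**What to change.** In the pilot paragraphs of Sections 6.0 and 7.0:

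- Base any claim of a navigation effect on a between-arm comparison, reported as non-randomised. Compare the change from first to second assessment between arms, and report beside it the second assessment adjusted for the baseline outcome and baseline characteristics.
- State what each assumes. Difference in change needs equal drift in both arms. The adjusted contrast also needs similar baselines, or covariates that explain the gap.
- Keep the matched-pair change as descriptive, shown separately by arm.
- Restate power for the between-arm comparison, with the 20% defined as percentage points and a dropout allowance.
- Make the reference to three time points agree with the test, and confirm that the baseline and 4-week assessments in Section 9.0 L apply to controls.

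Section 3.0 planned for the pilot to end in September 2020, so for data already collected this is a change to analysis and reporting. State how many controls were enrolled and assessed. If there were too few, report pre/post change without claiming a navigation effect.

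The cost is wording and reanalysis, with no new data collection. Stated power for difference in change is lower: below 0.83 at r = 0 and 0.3 without dropout, and below 0.83 at every correlation shown with 20% dropout. The adjusted contrast, given equal baselines, stays above 0.83 without dropout but falls to 0.78 at the low end with it. Residual selection bias remains under either analysis.
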